### 9.2.2 Metabolic Change

In addition to mean change from baseline, incidence of treatment emergent significant changes in fasting lipids, fasting glucose, and metabolic syndrome will be summarized by treatment group using the following criteria.

Criteria for Treatment-Emergent Significant Change in Lipids and Glucose		
LAB PARAMETER	BASELINE 	ANYTIME POST BASELINE
LDL Direct, Fasting (MG/DL)	Borderline 100-<160	High >=160
	Normal/Borderline <160	High >=160
	Normal <100	Borderline/High >=100
	Any Value	Increased >=30
HDL Cholesterol, Fasting (MG/DL)	Normal >=40	Low <40
	Any Value	Decreased >=20
Triglycerides, Fasting (MG/DL)	Normal <150	High 200-<500
	Borderline 150-<200	High 200-<500
	Normal/Borderline <200	High 200-<500
	Normal <150	Borderline/High/Very High >=150
	Any Value	Increased >=50
Glucose Fasting, Serum (MG/DL)	Normal <100	High >=126
	Impaired 100-<126	High >=126
	Normal/Impaired <126	High >=126
	Any Value	Increased >=10

 BASELINE IS CALCULATED FROM WEEK 1.

Criteria for Treatment-Emergent Metabolic Syndrome	
DESCRIPTION	ANYTIME POST BASELINE 
Central Obesity	Waist Circumference >=102cm(MALE), >=88cm (FEMALE)
Dyslipidemia	Triglycerides >= 150mg/dl
Dyslipidemia	HDL < 40mg/dl (MALE), <50mg/dl (FEMALE)
Supine Blood Pressure	Systolic >=130mmHg and Diastolic >=85mmHg
Glucose Fasting, Serum	>=100mg/dl
Metabolic Syndrome	Met 3 Or More of the Above Criteria at a Visit

 BASELINE IS CALCULATED FROM WEEK 1.

SAP 331-201-00080

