3.7 Trial Procedures

This trial is a phase 3, double-blind, placebo-controlled trial to investigate the efficacy, safety, and tolerability of brexpiprazole (2-4 mg/day) for the treatment of subjects with bipolar I disorder experiencing a manic episode with or without mixed features. The trial comprises a 3-week, double-blind treatment period with a 21 (\pm 2) day follow-up.

Trial assessment time points are summarized in [Table 3.7.1](#).

Protocol 331-201-00080

Table 3.7-1 Schedule of Assessments

	Screening ^a	Double-blind Treatment Phase					Follow-up ^c
	Day -14 to -1	Baseline (Day 1)	Day 4 (± 1 day)	Day 7 (± 1 day)	Day 14 (± 1 day)	Day 21/ET ^b (± 2 days)	21 (± 2) days after last dose
Screening Assessments and Randomization							
Informed Consent ^d	X						
Demographics	X						
Medical History	X						
Psychiatric History	X						
MINI	X						
Concomitant Medications ^e	X	X	X	X	X	X	X
Inclusion/Exclusion Criteria	X	X					
Randomization		X					
Efficacy Assessments							
YMRS ^f	X	X	X	X	X	X	
CGI-BP ^g		X	X	X	X	X	
CCI ^h		X	X		X	X	
Safety Assessments							
Physical Examination ⁱ	X					X	
Vital Signs ^j	X	X	X	X	X	X	
Body Weight	X					X	
12-lead ECG ^j	X	X				X	
Clinical laboratory tests (hematology, serum chemistry, urinalysis), including prolactin ^k	X					X	
HbA1c ^j	X					X	

Protocol 331-201-00080

Table 3.7-1 Schedule of Assessments

	Screening ^a	Double-blind Treatment Phase					Follow-up ^c
	Day -14 to -1	Baseline (Day 1)	Day 4 (± 1 day)	Day 7 (± 1 day)	Day 14 (± 1 day)	Day 21/ET ^b (± 2 days)	21 (± 2) days after last dose
TSH, with reflex to T4 if TSH is abnormal	X					X	
Coagulation parameters (PT, aPTT, INR) ^k	X					X	
Lithium, Valproate, Carbamazepine Levels ^l	X						
HIV, HBsAg, and anti-HCV	X						
Pregnancy Test ^m	X		X			X	
Drug Screen ⁿ	X					X	
Blood Alcohol Test ⁿ	X					X	
C-SSRS ^o	X	X	X	X	X	X	
CCl							
AEs ^p	X	X	X	X	X	X	X
CCl							
Other							
IMP dispensing ^r		X	X	X	X		
IMP accountability			X	X	X	X	

Protocol 331-201-00080

aPTT = activated partial thromboplastin time; HBsAg = Hepatitis B surface antigen; Anti-HCV = Antibodies to hepatitis C virus; INR = International Normalized Ratio; T4 = free thyroxine; TSH = thyroid-stimulating hormone.

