^aScreening begins when the ICF is signed and will take place between Day -14 and Day -1; however, screening procedures should be initiated with a sufficient amount of time allotted in order to obtain laboratory results and ECG results from the central reader prior to randomization. Review of inclusion/exclusion criteria at baseline will be based on assessments performed during screening. Hospitalization will begin with the signing of the ICF for subjects who are not already hospitalized at the initial screening visit. Note: In the rare circumstance when a subject must leave the inpatient facility temporarily (eg, family emergency or doctor visit), a temporary day pass may be granted. For such a request, sites must first contact the medical monitor for explicit authorization and guidance on procedures. A medical monitor approved day pass is good for the day requested only, and subjects must return to the site the same day (eg, in the evening).

^bIf a subject discontinues prematurely before Day 21, procedures noted for Day 21 must be completed at the ET visit.

^cConsists of telephone contact or clinic visit (investigator's discretion) for evaluation of safety 21 days after the last dose of IMP and applies only to subjects who do not enter the optional open-label rollover trial.

^dInformed consent must be obtained prior to any trial-related procedures. CCI [REDACTED]

^eAll medications taken within 30 days of screening will be recorded. In addition, all prescription and non-prescription medications taken during the trial will be recorded as concomitant medications.

^fTo be eligible for the trial, subjects must have a YMRS score ≥ 24 at screening and baseline.

CCI [REDACTED]

^hTo include measurement of height at screening only and waist circumference at screening and Day 21.

ⁱVital signs include body weight, body temperature, systolic blood pressure (SBP), diastolic blood pressure (DBP), and heart rate. Blood pressure and heart rate will be measured in the following order: supine and standing after the subject has been in each position for at least 3 minutes. Vital signs scheduled for the same visit as blood samples are to be completed before blood is drawn.

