3.7.1.2 Baseline (Day 1)

If the subject continues to be eligible for the trial after the screening period, the following procedures will be performed:

- An assessment of all inclusion and exclusion criteria will be made to confirm the subject's eligibility for the trial.
- A qualified and certified rater will administer the YMRS, CGI-BP, **CCI** [REDACTED]
[REDACTED] [REDACTED]
- The investigator (or qualified designee) who is adequately trained will complete the "Baseline/Screening" C-SSRS form.
- Vital sign measurements (body temperature, blood pressure, and heart rate) will be recorded. Blood pressure and heart rate are to be measured in the following order: supine and standing after the subject has been in each position at least 3 minutes. See [Table 3.4.3-1](#) for exclusions based on outcome of screening vital sign measurements.
- A standard 12-lead ECG will be performed after the subject has been supine and at rest for at least 5 minutes. See [Table 3.4.3-1](#) for exclusions based on ECG results.
- Adverse events and concomitant medications will be recorded.

Protocol 331-201-00080

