3.7.1.3 Randomization

Once subject eligibility has been confirmed at baseline, the following will be performed on Day 1:

- Trial personnel will access the IWRS or equivalent to register the visit and to obtain blister card assignment(s) for double-blind IMP. The assigned IMP will be dispensed to the subject.

3.7.1.4 Treatment Phase - Day 4

The following procedures will be performed on Day 4 (\pm 1 day):

- A qualified and certified rater will administer the YMRS and CGI-BP.
- The investigator (or qualified designee) who is adequately trained will complete the “Since Last Visit” C-SSRS form.
- **CCI**
[REDACTED]
- Vital sign measurements (body temperature, blood pressure, and heart rate) will be recorded. Blood pressure and heart rate are to be measured in the following order: supine and standing after the subject has been in each position at least 3 minutes.
- A urine pregnancy test will be performed for all WOCBP. All positive results must be confirmed by a serum pregnancy test. Subjects with a positive serum pregnancy test result will be withdrawn from the trial.
- Adverse events and concomitant medications will be recorded.
- IMP will be dispensed to the subject (Days 4, 5, and 6).
- Drug accountability will be performed.

3.7.1.5 Treatment Phase - Day 7

The following procedures will be performed on Day 7 (\pm 1 day):

- A qualified and certified rater will administer the YMRS and CGI-BP.
- The investigator (or qualified designee) who is adequately trained will complete the “Since Last Visit” C-SSRS form.
- **CCI**
[REDACTED]
- Vital sign measurements (body temperature, blood pressure, and heart rate) will be recorded. Blood pressure and heart rate are to be measured in the following order: supine and standing after the subject has been in each position at least 3 minutes.
- Adverse events and concomitant medications will be recorded.

Protocol 331-201-00080

- IMP will be dispensed to the subject (Days 7 through 13).
- Drug accountability will be performed.

3.7.1.6 Treatment Phase - Day 14

The following procedures will be performed on Day 14 (\pm 1 day):

- A qualified and certified rater will administer the YMRS, CGI-BP, CCI [REDACTED]
- The investigator (or qualified designee) who is adequately trained will complete the “Since Last Visit” C-SSRS form.
- CCI [REDACTED]

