3.7.1.7 End of Treatment Phase - Day 21/Early Termination Visit

All subjects will undergo a complete evaluation at Day 21 (\pm 2 days). In addition, Day 21 evaluations are to be completed for any subject withdrawn at any time after randomization into the trial. Attempts should be made to complete all evaluations, particularly efficacy assessments, for the Day 21/ET visit prior to the administration of any new psychotropic medications. However, if the subject receives a new rescue medication for worsening manic symptoms prior to ET procedures prior to the Day 21/ET procedures, no efficacy assessments should be performed.

The following procedures will be performed on Day 21(\pm 2 day) or the ET visit:

- A qualified and certified rater will administer the YMRS, CGI-BP, CCI [REDACTED]

Protocol 331-201-00080

- The investigator (or qualified designee) who is adequately trained will complete the “Since Last Visit” C-SSRS form.
- **CCI** [REDACTED]
- A complete physical examination will be performed.
- Vital sign measurements (body weight, body temperature, blood pressure, and heart rate) will be recorded. Blood pressure and heart rate are to be measured in the following order: supine and standing after the subject has been in each position at least 3 minutes.
- A standard 12-lead ECG will be performed after the subject has been supine and at rest for at least 5 minutes.
- Blood samples for clinical laboratory tests (hematology, coagulation parameters, and serum chemistry, including prolactin, HbA1c, and thyroid-stimulating hormone [TSH] with reflex to T₄ if the result for TSH is abnormal) must be drawn after a minimum 8-hour fast.
- Samples will be obtained for blood alcohol testing.
- Urine will be collected from subjects for urinalysis and urine screen(s) for drugs of abuse.
- A urine pregnancy test will be performed for all WOCBP. All positive results must be confirmed by a serum pregnancy test.
- **CCI** [REDACTED]
- **CCI** [REDACTED]
- Adverse events and concomitant medications will be recorded.
- Trial personnel will access the IWRS or equivalent to register the visit.
- Drug accountability will be performed.

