## **7 Baseline Characteristics**

### **7.1 Baseline Definition**

For analyses of the double-blind treatment period data, the baseline is the Baseline measurement (expected to be at Day 1). Baseline measurement is defined as the last available measurement prior to the start of double-blind IMP.

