## 9 Safety Analysis

Standard safety variables to be analyzed include Adverse Events (AEs), clinical laboratory tests, vital signs, body weight, waist circumference, BMI, 12-lead electrocardiograms (ECGs), and physical examinations. CCI

and Columbia-Suicide Severity Rating Scale (C-SSRS).

SAP 331-201-00080

Safety analysis will be conducted based on the Safety Sample unless indicated otherwise. In general, baseline of a safety variable is defined as the last observation of the variable before taking the first dose of IMP, unless specified otherwise. Prospectively defined criteria will be used to identify potentially clinically relevant abnormal values for clinical laboratory tests, vital signs, ECGs, and body weight.

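### SAP 9.2.2 takes the metabolic baseline from Week 1, when no lipid, glucose or waist value is scheduled, and its treatment-emergent metabolic syndrome rule counts cases that were present before dosing

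*SAP*

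**What the plan says.** SAP 9.2.2 plans to summarize, by treatment group, the incidence of treatment-emergent change in fasting lipids, fasting glucose and metabolic syndrome. It defines these in two tables. The lipid and glucose table has a baseline column and a post-baseline column. The metabolic syndrome table has only a description and a post-baseline column; a subject qualifies by meeting at least three of five criteria (waist, triglycerides, HDL, supine blood pressure, fasting glucose) at one visit. Both tables carry the footnote "BASELINE IS CALCULATED FROM WEEK 1".

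Elsewhere the SAP defines baseline differently. Section 7.1 says: "Baseline measurement is defined as the last available measurement prior to the start of double-blind IMP". Section 9 says that, in general, "baseline of a safety variable is defined as the last observation of the variable before taking the first dose of IMP", but allows exceptions where specified.

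In Protocol Table 3.7-1, the row "Clinical laboratory tests (hematology, serum chemistry, urinalysis), including prolactin" is marked at Screening and Day 21/ET only. Footnote h to that table places "waist circumference at screening and Day 21".

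**The concern.** There are two separate faults.

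First, the footnote names a period in which most of the required data are not collected. Read literally, it leaves the lipid, glucose and waist baselines missing. Where an early-termination or unscheduled draw happens to fall in Days 1-7, it would make a post-dose value the baseline.

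Second, the syndrome table is labelled treatment-emergent but sets no condition on baseline status. Followed as written, it reports post-baseline prevalence under the name of emergent incidence. Pre-existing cases are to be expected: exclusion criterion 17 admits stable non-insulin diabetes with a fasting screening glucose up to 125 mg/dL, while the syndrome cut-off is 100 mg/dL, and criterion 16 sends severe obesity to the medical monitor for discussion and does not exclude it outright. Safety is the trial's secondary objective, and a metabolic signal could be diluted or distorted in this table.

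**Working it through.** SAP 9.2.2 states no figure to reproduce. The check has three parts.

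**1. Schedule against Week 1.** The only definition of Week 1 in the SAP is Days 1-7, given for dosing weeks in section 9.9.

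- Day 1 (Protocol 3.7.1.2): "Vital sign measurements (body temperature, blood pressure, and heart rate) will be recorded", plus an ECG. There is no blood draw and no waist measurement.
- Day 4 (Protocol 3.7.1.4): "A urine pregnancy test will be performed for all WOCBP". This is the only laboratory test listed at Day 4 or Day 7.
- Day 21/ET (Protocol 3.7.1.7): chemistry "must be drawn after a minimum 8-hour fast". This is the only scheduled post-dose chemistry draw.

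Scheduled Week 1 measurements are therefore 0 for lipids and glucose, 0 for waist, and 3 for supine blood pressure (Days 1, 4 and 7). None of the four parameters in the lipid and glucose table has a scheduled Week 1 value, and only one of the five syndrome criteria does. Reading Week 1 as the Day 1 visit changes nothing for lipids, glucose or waist.

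**2. The syndrome rule applied to an unchanged subject.** Take a man with waist 105 cm, triglycerides 180 mg/dL, HDL 38 mg/dL, blood pressure 120/75 mmHg and fasting glucose 95 mg/dL, both before dosing and at Day 21. He meets three criteria (waist, triglycerides, HDL) each time. As written he is treatment-emergent; with a not-at-baseline condition he is not.

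**3. Size.** Let P0 be baseline prevalence, q the proportion of baseline cases still meeting the rule after dosing, and n the new-onset rate among subjects without the syndrome at baseline. Then

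tabulated rate = q × P0 + (1 − P0) × n.

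The documents give none of these inputs, so all are assumed. With q = 0.90 in both arms (drug v placebo; each cell shows the tabulated rates in %, then their ratio):

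| P0 | n = 5% v 2% (true ratio 2.5) | n = 10% v 5% (true 2.0) | n = 3% v 2% (true 1.5) |
|---|---|---|---|
| 5% | 9.25 v 6.40; 1.45 | 14.0 v 9.25; 1.51 | 7.35 v 6.40; 1.15 |
| 20% | 22.0 v 19.6; 1.12 | 26.0 v 22.0; 1.18 | 20.4 v 19.6; 1.04 |
| 40% | 39.0 v 37.2; 1.05 | 42.0 v 39.0; 1.08 | 37.8 v 37.2; 1.02 |

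Example, P0 = 20%, n = 5%: 0.90 × 0.20 + 0.80 × 0.05 = 0.18 + 0.04 = 22.0%. The pre-existing share of those cases is 0.18 / 0.22 = 82%; at P0 = 5% and 40% it is 49% and 92%. Varying q from 0.8 to 1.0 moves the first column's ratios only to 1.48-1.41, 1.14-1.11 and 1.05-1.04.

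The difference between arms is (1 − P0) × (nD − nP) + P0 × (qD − qP), where D is drug and P placebo. It equals the new-onset part alone only if persistence is the same in both arms. In percentage points:

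| P0 | n = 5% v 2%, equal q | q = 95% v 85% | q = 85% v 95% | n = 3% in both arms, q = 95% v 85% |
|---|---|---|---|---|
| 5% | 2.85 | 3.35 | 2.35 | 0.5 |
| 20% | 2.40 | 4.40 | 0.40 | 2.0 |
| 40% | 1.80 | 5.80 | −2.20 | 4.0 |

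The last column shows a difference between arms when there is no effect on new onset at all.

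**The case against.** **On the footnote.** SAP 9 permits exceptions, and a table footnote can be one. The footnote also cannot be carried out for nearly all subjects, so a programmer would notice and probably use the screening value. Both points are fair, and they make the first fault a contradiction to reconcile more than a likely error in the output. But SAP 7.1 contains no exception, the two sections do not say which governs, and no exception clause creates measurements that were never scheduled.

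**On the syndrome rule.** The section's opening sentence and the table title both say treatment-emergent, so a sensible reader might exclude baseline cases. The SAP is not uniform either: most laboratory criteria in its Appendix 2 have no baseline condition, and its adverse event definition lets some events continuing from baseline count. This does not supply the missing condition. Appendix 2 is not labelled emergent, and the adverse event rule admits continuing events only on listed grounds such as worsening or seriousness. Where the SAP means new onset it says so: the QT/QTc new-onset rows in section 9.4 and the suicidality emergence rules in section 9.7 require absence at baseline. For orthostatic hypotension, Appendix 1 states outright that baseline is not considered.

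**On consequence.** No risk ratio is planned, and with equal persistence the difference between arms is preserved as the new-onset difference over all subjects. That stands. Mean changes, the baseline-conditioned lipid and glucose shifts and the separate weight and waist analyses also give some protection, although the shift table depends on the same faulty baseline footnote. The 40% prevalence and the unequal persistence figures have no support in the documents and serve only to show the range.

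**Conclusion.** Both faults hold. The Week 1 footnote cannot be executed for lipids, glucose or waist and contradicts SAP 7.1. The syndrome rule, followed as written, counts unchanged pre-existing cases as treatment-emergent.

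The direction of the second fault needs little assumption: with any nonzero baseline prevalence and equal, nonzero persistence, rates in each arm describe post-baseline prevalence, and a real risk ratio is pulled toward 1. Its size depends entirely on assumed inputs. Over the equal-persistence range shown, a true ratio of 2.5 appears as 1.45 to 1.05. Under the unequal-persistence scenarios, a new-onset contribution of 1.80 to 2.85 points is tabulated as anything from −2.20 to 5.80.

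The reach is limited to descriptive safety tables; no efficacy test is affected. This should be fixed, and the syndrome rule matters more than the footnote.

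**What to change.** 1. Replace the footnote on both tables with the SAP 7.1 and SAP 9 baseline: the last value before the first dose of double-blind IMP, which for lipids, glucose and waist is normally screening. Report by arm how many subjects lack a fasting pre-dose value.
2. Count metabolic syndrome as treatment-emergent only in subjects with fewer than three criteria at baseline, and use those subjects as the denominator, since the others cannot become new cases. Show subjects whose baseline status cannot be determined as not evaluable.
3. If post-baseline prevalence is also wanted, tabulate it separately under that name.

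These are wording edits to SAP 9.2.2 and need no new data. The list of summary tables in SAP 13 is blacked out, so whether its titles also need changing cannot be checked.

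The syndrome denominator shrinks: 160 × (1 − P0) gives 152, 128 or 96 per arm at 5%, 20% or 40% assumed prevalence. Subjects whose only pre-dose sample was nonfasting, which footnote k to Protocol Table 3.7-1 permits at screening, drop out of the fasting rows; their number is not given.

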18.	
Subjects with uncontrolled hypertension (DBP > 95 mmHg in any position) or symptomatic hypotension, or orthostatic hypotension which is defined as a decrease of ≥ 30 mmHg in SBP and/or a decrease of ≥ 20 mmHg in DBP after at least 3 minutes standing compared to the previous supine blood pressure, OR development of symptoms.
 
NOTE: Blood pressure measurements may be repeated once to ensure reproducibility of the exclusionary result(s) before excluding a subject based on the criteria noted above.

19.	Subjects with epilepsy or a history of seizures, except for a single seizure episode; for instance childhood febrile, post traumatic, or alcohol withdrawal seizure.
20.	Subjects with a history of a gastric bypass surgery that creates a malabsorptive state, including Roux-en-Y gastric bypass and biliopancreatic bypass with duodenal switch. This does not include gastric banding, gastric stapling, and sleeve gastrectomy procedures.

Protocol 331-201-00080

Table 3.4.3-1 Exclusion Criteria

Physical and Laboratory Results	
21.	Subjects with abnormal laboratory tests results, vital signs results, or ECG findings, unless, based on the investigator's judgment, the findings are not medically significant and would not impact the safety of the subject or the interpretation of the trial results. The medical monitor should be contacted to discuss individual cases, as needed. Criteria are provided in Section 3.7.3.2 . In addition, subjects with the following laboratory test and ECG results at screening must be excluded from the trial: 
 • Platelets \leq 75000/mm³ • Hemoglobin \leq 9 g/dL • Neutrophils, absolute \leq 1000/mm³ • AST $>$ 2 \times ULN • ALT $>$ 2 \times ULN • CPK $>$ 3 \times ULN, unless discussed with and approved by the medical monitor • Creatinine \geq 2 mg/dL • QTcF \geq 450 msec in men and \geq 470 msec in women, unless due to ventricular pacing. 
Tests with exclusionary results should be repeated to ensure reproducibility of the abnormality before excluding a subject based on the criteria noted above. For ECG, perform 3 consecutive recordings. If 2 of the 3 remain exclusionary then the subject must be excluded.

Disallowed and Concomitant Medication	
23.	Recent treatment with a long acting or depot antipsychotic in which the last dose was less than one full cycle plus 1/2 cycle from baseline visit (Section 4.1).

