## 12 Potential Clinical Relevance Criteria from Protocol

### Appendix 1 Criteria for Identifying Vital Signs of Potential Clinical Relevance

Variable	Criterion Value a	Change Relative to Baseline a
Heart Rate b	> 120 bpm < 50 bpm	≥ 15 bpm increase ≥ 15 bpm decrease
Systolic Blood Pressure b	> 180 mmHg < 90 mmHg	≥ 20 mmHg increase ≥ 20 mmHg decrease
Diastolic Blood Pressure b	> 105 mmHg < 50 mmHg	≥ 15 mmHg increase ≥ 15 mmHg decrease
Orthostatic Hypotension	≥ 20 mmHg decrease in systolic blood pressure and a ≥ 25 bpm increase in heart rate from supine to sitting/standing	Not Applicable (baseline status not considered)
Weight	-	≥ 7% increase ≥ 7% decrease

a In order to be identified as potentially clinically relevant, an on-treatment value must meet the “Criterion Value” and also represent a change from the subject’s baseline value of at least the magnitude shown in the “Change Relative to Baseline” column.

b As defined in “Supplementary Suggestions for Preparing an Integrated Summary of Safety Information in an Original NDA Submission and for Organizing Information in Periodic Safety Updates,” FDA Division of Neuropharmacological Drug Products draft (2/27/87).

SAP 331-201-00080

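### The metabolic-syndrome blood-pressure component needs systolic and diastolic pressure raised together, so an isolated elevation does not count

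*SAP*

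**What the plan says.** SAP 9.2.2 (Metabolic Change) states that the incidence of changes in fasting lipids, "fasting glucose, and metabolic syndrome will be summarized by treatment group using the following criteria". The syndrome table lists five components: waist circumference, triglycerides, HDL, supine blood pressure and fasting glucose. The blood-pressure row reads "Systolic >=130mmHg and Diastolic >=85mmHg". The syndrome itself is "Met 3 Or More of the Above Criteria at a Visit". The only footnote is "BASELINE IS CALCULATED FROM WEEK 1"; the table has a post-baseline column and states no baseline condition. No note gives an either/or reading of the blood-pressure row.

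Three other places bear on the point:

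- **Exclusion 18 (Protocol 3.4.3)** bars "Subjects with uncontrolled hypertension (DBP > 95 mmHg in any position", together with symptomatic and orthostatic hypotension. It sets no systolic ceiling.
- **SAP Appendix 1** has separate rows for systolic ("> 180 mmHg < 90 mmHg") and diastolic pressure ("> 105 mmHg < 50 mmHg"). Each row qualifies alone, with a change from baseline.
- **Protocol 3.7, schedule of assessments:** "Blood pressure and heart rate will be measured in the following order: supine and standing". The supine pair is taken at every visit. Laboratory tests and waist circumference are scheduled only at screening and Day 21/ET.

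**The concern.** The blood-pressure row is the only one in its table that needs two measurements to be abnormal together. The two lipid abnormalities even have separate rows, so each counts alone. Yet a supine pressure of 125/96 at Day 21 would not score, although exclusion 18 would call the same diastolic value uncontrolled hypertension at entry.

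At stake is the incidence in a pre-specified safety table. A subject with exactly two other components is classified by blood pressure alone, so the connector in this row decides whether that subject is a case. Because laboratory tests and waist are scheduled only once after baseline, an isolated elevation missed at Day 21/ET has no later scheduled visit at which it could contribute.

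**Working it through.** The plan gives no rate, sample size or power for metabolic syndrome, so there is no figure of its own to reproduce.

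**Step 1: direction.** Let S be supine systolic >=130 and D supine diastolic >=85. Then P(S or D) = P(S) + P(D) - P(S and D), and the subjects with both raised are a subset of those with either raised. The post-baseline syndrome count under 'and' therefore cannot exceed the count under 'or'. The two differ by exactly the subjects who have two other components plus an isolated elevation.

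For new cases the ordering is not certain. Take a subject with two other components throughout, an isolated elevation at baseline and both pressures raised at Day 21. That subject is a new case under 'and', but already a case at baseline under 'or'.

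**Step 2: size of the component (all inputs assumed).** Supine SBP mean 118-126, SD 12-15; DBP mean 75-80, SD 9-10; correlation r 0.6-0.8; bivariate normal. With a = (130 - mean SBP)/SD and b = (85 - mean DBP)/SD, P(S) = 1 - Φ(a), P(D) = 1 - Φ(b), and P(S and D) is the bivariate-normal upper tail.

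| SBP mean (SD) | DBP mean (SD) | r | P(S) | P(D) | both | either |
|---|---|---|---|---|---|---|
| 118 (12) | 75 (9) | 0.6 | 0.159 | 0.133 | 0.064 | 0.228 |
| 118 (12) | 75 (9) | 0.8 | 0.159 | 0.133 | 0.088 | 0.204 |
| 126 (15) | 80 (10) | 0.6 | 0.395 | 0.309 | 0.211 | 0.492 |
| 126 (15) | 80 (10) | 0.8 | 0.395 | 0.309 | 0.251 | 0.453 |

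These rows give the extremes over a grid of the assumed ranges: 'and' flags 6%-25%, 'or' 20%-49%. Across the grid, 'and' leaves out 44%-75% of subjects with a raised pressure.

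**Step 3: size of the syndrome (all inputs assumed).** The other four components were taken as independent of each other and of blood pressure. Then P(syndrome) = P(3 or more others) + P(exactly 2 others) × P(blood-pressure component).

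- Others at 40%, 30%, 35% and 30%: P(3 or more) = 0.1137 and P(exactly 2) = 0.3011. With SBP 120 (12), DBP 76 (9) and r = 0.6, the component is 0.085 ('and') or 0.276 ('or').
  - 'and': 0.1137 + 0.3011 × 0.085 = 0.139
  - 'or': 0.1137 + 0.3011 × 0.276 = 0.197
- Others at 50%, 40%, 40% and 40%: P(3 or more) = 0.208 and P(exactly 2) = 0.36. With SBP 126 (14), DBP 80 (10) and r = 0.6, the component is 0.209 or 0.487.
  - 'and': 0.208 + 0.36 × 0.209 = 0.283
  - 'or': 0.208 + 0.36 × 0.487 = 0.383

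A simulation of 1,000,000 subjects per scenario agrees with this. It adds a baseline visit, with an assumed baseline-to-Day-21 correlation:

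| SBP/DBP mean | visit correlation | post-baseline, and / or | new among those free at baseline, and / or |
|---|---|---|---|
| 120/76 | 0.7 | 14.0% / 19.7% | 9.7% / 13.3% |
| 122/78 | 0.7 | 15.3% / 22.2% | 10.5% / 14.8% |
| 126/80 | 0.7 | 28.4% / 38.5% | 18.5% / 24.7% |
| 126/80 | 0.9 | 28.3% / 38.4% | 12.2% / 16.2% |

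The 122/78 row uses SD 13 and 9 and the first set of component prevalences.

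**The case against.** The strongest reply is that the documents cite no reference definition of metabolic syndrome, so nothing in them makes either/or the correct rule. That stands: the count is low relative to an either/or rule, not against a definition the plan adopted. The case for changing the row rests on its mismatch with its neighbours and with exclusion 18.

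The other comparisons have limits. Appendix 1 flags extreme values that also need a change from baseline, and exclusion 18 is an entry rule. Neither defines a syndrome component, so the difference is an inconsistency of approach rather than a contradiction. The connector may also be loose wording. In the QTc table of SAP 9.4 the category label joins the male and female limits with 'and', while its criterion text uses 'or'. If the blood-pressure row was meant as either/or, it still needs correcting, because it can be programmed as written.

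The consequence is bounded. Section 9.2.2 plans a summary by treatment group, with no test of metabolic syndrome. Change from baseline in vital signs is summarised separately (SAP 9.3).

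Two stronger inferences are tempting and not supported. A reader might conclude that subjects with isolated systolic elevation are expressly admitted. Exclusion 18 is only silent on systolic pressure, and exclusion 21 and Protocol 3.7.3.3.2 leave other abnormal vital signs to the investigator's judgment. A reader might also infer that the joint rule blunts the comparison between arms. It applies equally to both arms, and no between-arm difference or precision was computed under either rule, so that loss is not shown.

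**Conclusion.** The point holds as a definitional one. As written, the row excludes isolated systolic or diastolic elevation, and the post-baseline count of metabolic syndrome is equal to or lower than under an either/or rule. That direction needs no assumption. For new cases among subjects free of the syndrome at baseline, a lower count is likely, and it appeared in all four simulated scenarios, but it is not guaranteed. The table does not say whether absence at baseline is required.

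The size rests wholly on assumed inputs, including independence of the components. The component is about 6%-25% against 20%-49%; the syndrome about 14%-28% against 20%-38% post-baseline, and about 10%-19% against 13%-25% for new cases. The 44%-75% of raised pressures left out describes the component only and should not be read as the share of syndrome cases lost. The primary and key secondary analyses are untouched.

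**What to change.** In SAP 9.2.2, change the row to 'Systolic >=130 mmHg or Diastolic >=85 mmHg', leave the other components as they are, and align the table programming. If the joint requirement is intended, the sponsor should say so and justify it, so that the text and the program cannot diverge.

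The cost is one word and one line of code, and the supine pressures are already collected. The downside is that the reported incidence becomes somewhat higher in both arms.
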